All primary analyses will be based on modified intention-to-treat (mITT) principle (i.e., all identified early intervention patients who met eligibility and were mailed the intervention will be included; using “pseudo” wave assignments, all identified delayed intervention patients who met eligibility at the time of corresponding early mailings will be included). Since the additional exclusions after randomization will be applied in the same way, using the same time points for both the early and delayed intervention groups, we expect there will be no effect from these additional exclusions on the randomization. The mITT analysis will include the following:

- Early intervention members who were mailed a letter, with follow-up beginning on the date of mailing (up to two dates per site and the dates varied by site).
- Delayed intervention members who were not on treatment at the date of mailing (wave assignments were made for the delayed as described earlier in section I.F) with follow-up beginning on that date.

An as-randomized analysis will be performed for an incident occurrence of the primary endpoint as a sensitivity analysis (using a washout of 365 days). Randomization occurred prior to treatment status assessment per the study design. Therefore, the as-randomized analysis will include people who were on treatment as well as others who were not truly eligible for the study (e.g., had incomplete or invalid addresses or had a “do not contact” status).

Potential sensitivity analysis for mITT analysis: There may be differential loss to follow up between the early and delayed intervention groups because some members did not have valid mailing addresses, though we did not assess the addresses of the members in the delayed intervention arm at the time of early intervention mailings. It is not possible to retrospectively ascertain the address status of the delayed intervention group as of the date on which mailing would have occurred for that group. We can estimate the magnitude by referring to the early intervention group, and in the early intervention group, we can compare the baseline characteristics and experience of the individuals who had no valid address to those who do.

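### The primary set leaves unmailed members out of the early arm only, so the SAP's claim of equal post-randomization exclusions is wrong for address status

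*SAP*

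**What the plan says.** Three statements stand close together at the start of SAP section II.

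- **Symmetry.** The SAP says that "additional exclusions after randomization will be applied in the same way, using the same time points for both the early and delayed intervention groups", and concludes that the randomization should be unaffected.
- **Entry rules.** The early arm consists of "Early intervention members who were mailed a letter, with follow-up beginning on the date of mailing". The delayed arm consists of "Delayed intervention members who were not on treatment at the date of mailing"; in the general definition, "all identified delayed intervention patients who met eligibility at the time of corresponding early mailings will be included". Protocol XIV.B sets the same two rules: mailing is a condition in the early arm only.
- **Addresses.** Under a potential sensitivity analysis the SAP names the problem: "There may be differential loss to follow up between the early and delayed intervention groups because some members did not have valid mailing addresses". For the delayed arm, the SAP concedes that no check was made, and that the gap cannot be closed later: "It is not possible to retrospectively ascertain the address status of the delayed intervention group".

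Protocol IX lists a bad address among the reasons a letter may not go out. SAP I.F removes from both arms anyone who dies, disenrolls or starts OAC between randomization and mailing; address is not on that list. SAP II also plans an as-randomized analysis of the incident primary endpoint with a 365-day washout. It takes in people already on treatment and "others who were not truly eligible for the study (e.g., had incomplete or invalid addresses".

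**The concern.** An exclusion that can be made in only one arm removes the balance that randomization provides. Early-arm members without a valid address never enter the primary set, while their counterparts stay in the delayed arm. Calling this loss to follow-up misplaces it: these members have no follow-up to lose, and censoring rules cannot address it.

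The primary comparison is very precise, with a standard error near 0.4 percentage points at the planned size, so a small selection effect can matter when the true effect is null or small. That case is plausible. Protocol X says there is no evidence yet that insurer letters of this kind change anticoagulant use. Protocol VI and SAP I.C also allow the 24-month analyses to be dropped if the primary result is null.

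**Working it through.** **Step 1. The mailing failures listed in Protocol IX, by arm**

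| Reason | Early arm | Delayed arm |
|---|---|---|
| Death, disenrollment, OAC start before mailing | Out (SAP I.F) | Out at the matching date (SAP I.F) |
| Bad address | Out, because not mailed | In; not assessed and not recoverable (SAP II) |
| Do-not-contact; plan that bars research | Out if not mailed | Unclear |

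The second row contradicts the symmetry statement.

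**Step 2. The plan's own figures.** SAP I.G assumes 33% against 38%, two-sided 0.05, 30% attrition. With a continuity correction, n per arm is 1963 / 2418 / 3401 for 90 / 95 / 99% power. Dividing by 0.70 gives 2805 / 3455 / 4859, as tabulated. The planned odds ratio is (0.38/0.62)/(0.33/0.67) = 1.24. The target of 80,000 gives 40,000 per arm, and 40,000 x 0.70 = 28,000. The point does not depend on the power table.

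**Step 3. Bias under no true effect.** Let f be the unmailed share, RR the OAC rate in unmailed relative to mailed patients, and pm the rate in mailed patients. The documents give neither f nor RR, so both are assumed. The delayed arm contains both kinds of patient, so (1-f)pm + f x RR x pm = 0.33. Hence:

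- pm = 0.33 / (1 - f + f x RR)
- bias = pm - 0.33
- SE = sqrt[ pm(1-pm)/(n(1-f)) + 0.33 x 0.67/n ]
- type I error = P(|Z + bias/SE| > 1.96)

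Example, f = 3%, RR = 0.75, n = 28,000: pm = 0.33/0.9925 = 0.3325; bias = +0.25 points; SE = 0.40 points; type I error = 9.5%.

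**Step 4. Range at 28,000 per arm: bias in points / two-sided type I error**

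| f | RR 0.5 | RR 0.75 | RR 1 | RR 1.25 | RR 2.0 |
|---|---|---|---|---|---|
| 1% | +0.17 / 7.0% | +0.08 / 5.5% | 0 / 5% | -0.08 / 5.5% | -0.33 / 13% |
| 3% | +0.50 / 24% | +0.25 / 9.5% | 0 / 5% | -0.25 / 9.4% | -0.96 / 67% |
| 5% | +0.85 / 55% | +0.42 / 17.9% | 0 / 5% | -0.41 / 17.3% | -1.57 / 98% |

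For ratios above 1 the excess rejections run against the intervention. The corner values need extreme assumptions on both inputs. Over the whole grid the odds ratio runs from 0.93 to 1.04.

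The analysis set may be smaller than 28,000 per arm, because Protocol IX applies the prior-OAC exclusion after randomization. At an assumed 14,000 per arm, f = 3% gives 14.4% at RR 0.5 and 7.2% at RR 0.75.

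**Step 5. Price of a symmetric set.** If 5% are unmailed and gain nothing, the effect is 0.95 x 5.0 = 4.75 points (37.75% against 33%), odds ratio 1.23. At 28,000 per arm SE = sqrt[(0.3775 x 0.6225 + 0.33 x 0.67)/28,000] = 0.40 points and z = 11.8. At 14,000 per arm z = 8.3. Power stays near 100%.

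**The case against.** The strongest reply is that the SAP already handles this.

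- **It is disclosed and can be estimated.** The SAP says that the magnitude can be gauged from the early arm, by comparing members with and without a valid address. That is sound: the bias equals f x (rate in mailed minus rate in unmailed), and by randomization the early arm estimates both parts, provided neither the unmailed members nor their providers were contacted. But the step is only potential, and the statement of no expected effect remains.
- **An as-randomized analysis is firmly planned (Tables 1S and 2S), as are CONSORT counts.** That analysis is a valid randomized comparison, and the washout may limit dilution. But it also includes people on treatment, so a difference from the primary result could not be traced to addresses.
- **Eligibility might cover it.** The SAP describes invalid-address members as not truly eligible, so the delayed-arm eligibility rule could be read as removing them. It cannot, since they cannot be identified.
- **The primary model is adjusted.** Table A has age, sex and medical history, but nothing on address, contact or region. Adjustment may remove part of the bias; nothing ensures that it removes all.

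A reader might also infer that do-not-contact status and loss of research eligibility are handled one-sidedly. The documents do not establish this. SAP II groups do-not-contact members with those not truly eligible, which could remove them from both arms. Against that, SAP I.F names only enrollment and treatment status for the delayed-arm check, and Protocol XIV.A lists being eligible and being contactable separately. For research eligibility, Protocol XIV.B censors at its loss; if that falls before the wave date no follow-up remains, which amounts to exclusion. This is an ambiguity, not a shown error.

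**Conclusion.** For address status the symmetry statement is wrong as written, and nothing else in the documents repairs it in the primary set. It should be fixed.

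A reader might infer that the gap could account for a positive trial, or that it favors the intervention. The documents support neither. Over the assumed grid (f 1-5%, RR 0.5 to 2.0, no true effect, 33% initiation, 28,000 per arm, unadjusted) the bias lies between +0.85 and -1.57 points, against a planned effect of 5 points. Its sign depends on an unknown ratio, and it vanishes if unmailed and mailed patients start OAC at the same rate. Provider clustering and pooling across Data Partners are not modeled. The practical risk is limited to a null or small true effect, where the gap could create or hide a nominally significant result. Nor is this concealment, since the SAP raises the gap itself.

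**What to change.** 1. **Correct the wording in SAP II.** State that mailing is required in the early arm only, withdraw the no-effect expectation for address status, and describe the gap as selection into the analysis set.
2. **Firmly pre-specify a symmetric analysis.** Keep otherwise eligible unmailed early-arm patients, start their follow-up on a wave date assigned by the same rule as the delayed pseudo-waves, and apply the SAP I.F exclusions to both arms at that date. This needs no delayed-arm addresses. Making it the primary set, with the mailed-only analysis as supportive, is the stronger option, but needs an amendment of Protocol XIV.B.
3. **Report** the number of early-arm patients not mailed, by reason, with their OAC rate.

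As a query only: say whether do-not-contact status and loss of research eligibility before the mailing date are applied in both arms or in neither.

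Cost: SAP text and one extra distributed run, with the program validation and testing that SAP II.A requires. The claims should be available, since the as-randomized set already includes members with invalid addresses. The statistical price is the slight dilution in Step 5.

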Among AF patients with guideline indications for OAC for stroke prevention who have not received any OAC dispensing for at least one year, an education intervention at the patient-level and the provider-level will increase the proportion of patients started on OAC for stroke prevention.

IV. STUDY RATIONALE

Preliminary data from three Sentinel Data Partners between 1/1/2006 and 6/30/2015, identified 231,696 patients (1.4%) with at least 2 diagnoses of AF (ICD-9 codes of 427.31 or 427.32) over the study period, among 16.2 million covered lives. Within the 231,696 AF patients, there were 201,882 with a CHA₂DS₂-VASc score of 2 or greater (based on administrative claims data in the Sentinel Distributed Database), which is an American Heart Association (AHA)/American College of Cardiology (ACC) guideline indication for OAC. Over the study period from 2006 through 2015, 52% (n=105,256) patients filled at least one prescription for anticoagulation, meaning that 48% of patients with CHA₂DS₂-VASc score of 2 or greater never had a pharmacy claim submitted for an OAC during the study period. While there may be clinical or health system related reasons for not treating some of these patients, this apparent significant gap of guideline-based adherence is a public health issue of interest. The presented protocol is an opportunity to test the potential for developing and testing a health plan (Data Partner) based education intervention to improve the quality of care.

V. STUDY OBJECTIVES

A. PRIMARY OBJECTIVE

The primary objective is to evaluate the effect of the patient and provider education interventions (versus usual care with delayed provider education intervention) on the proportion of patients with evidence of at least one OAC prescription fill (defined as one OAC dispensing or 4 INR tests) over the course of the follow-up through the date on which at least 80% of eligible study participants have at least 12 months of follow-up time.

B. SECONDARY OBJECTIVE

The secondary objectives are to evaluate the impact on outcomes of the patient and provider education interventions over the course of the follow-up through the date on which at least 80% of eligible study participants have at least 12 months of follow-up time:

- 1. Incident rate of stroke or transient ischemic attack (TIA) hospitalization
- 2. Incident rate of hospitalization for stroke
- 3. Time to first OAC prescription fill
- 4. Proportion of days covered by OAC prescription fills

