An electronic program, developed by the central coordinating center (Harvard Pilgrim), will be used by the participating Data Partners to identify their eligible member-patients who meet the inclusion and exclusion criteria for this trial. The patient billing claims records will not be linked to pharmacy data until after randomization, so the inclusion criterion of no OAC medication fill during the 12 months prior to randomization will not be applied until after randomization. This will be done immediately for the early intervention group, and in the delayed intervention group, not until 12 months after at least 80% of early intervention mailing have occurred. Patients will be randomly assigned in a 1:1 ratio, via the program, to early patient-level and provider-level intervention versus delayed provider-level intervention. A list of eligible member-patients will stay at each Data Partner, and identifiable patient-level data will not be shared with the central coordinating center (Harvard Pilgrim) or the statistical analysis center (Duke Clinical Research Institute). The Data Partners will remove any individuals who cannot be included in research studies, which includes certain Centers for Medicare and Medicaid Services and Administrative Services Only patients. There are several other reasons that could prevent mailing of the intervention, to members and/or their providers (list may not be exhaustive):

- Member is now deceased
- Member disenrolls from health plan
- Member transitions to a plan that does not allow for inclusion in research
- Member has a recent anticoagulant dispensing
- Member has an incorrect/missing/bad address
- Member is added to a do-not-contact list at the health plan

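### The as-randomized sensitivity analysis keeps patients already on OAC, so its odds ratio is attenuated by design and cannot be compared numerically with the mITT odds ratio

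*SAP*

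**What the plan says.** Patients were randomized before their OAC status was known. Protocol section IX states that "the inclusion criterion of no OAC medication fill during the 12 months prior to randomization will not be applied until after randomization", and SAP section II confirms that "Randomization occurred prior to treatment status assessment per the study design". The randomized set therefore contains current OAC users in both arms.

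SAP section II plans the as-randomized analysis "for an incident occurrence of the primary endpoint as a sensitivity analysis (using a washout of 365 days") and adds that "the as-randomized analysis will include people who were on treatment as well as others who were not truly eligible for the study". It does not say how the washout acts on the denominator, and it gives no follow-up start date for this analysis. Protocol section XIV.B also commits to an as-randomized analysis, without mentioning incident events or a washout. SAP Table 2S reports n/N by arm and odds ratios at 365 days.

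The primary mITT set is built differently in the two arms. The early arm is "Early intervention members who were mailed a letter, with follow-up beginning on the date of mailing". The delayed arm is those not on treatment on the corresponding date, with no address or contact filter named. The SAP acknowledges that "we did not assess the addresses of the members in the delayed intervention arm at the time of early intervention mailings" and that this cannot be recovered afterwards. By contrast, patients who die, disenroll or start OAC between randomization and mailing are to be removed from both arms (SAP section I.F).

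**The concern.** With a 365-day washout and a 365-day window, a regular user who filled shortly before follow-up began would need 365 fill-free days before a new fill could count. Almost nothing of the window would be left. Such patients add to N in both arms and hardly at all to n.

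The as-randomized analysis is the one committed between-arm estimate that does not depend on mailing. A reader will naturally hold its odds ratio against the mITT odds ratio to see whether the one-sided loss of bad-address and do-not-contact patients has moved the result. If one odds ratio is attenuated by OAC users, a gap between the two could reflect dilution, selection or both. No committed between-arm analysis removes the mailing asymmetry on the scale of the mITT estimate.

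**Working it through.** **1. The plan's own figure.** The SAP gives no expected result for the as-randomized analysis, so I checked the inputs against the primary sample-size table (SAP section I.G): 33% versus 38%, two-sided 0.05, 30% attrition. Protocol section XIV.A names the continuity-corrected chi-square. That formula gives 1,963, 2,418 and 3,401 per arm at 90%, 95% and 99% power. Dividing by 0.70 gives 2,805, 3,455 and 4,859, so totals of 5,610, 6,910 and 9,718, as tabulated. (The Protocol labels this table as not adjusted for dropout. The figures match only after the division.)

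**2. Dilution.** Let s be the share of randomized patients with prior-year OAC use, equal in the arms by randomization and treated as non-events. Each rate becomes (1 − s) × the eligible-patient rate. The value of s is an assumption. The nearest figure in the documents, in Protocol section IV, is that "52% (n=105,256) patients filled at least one prescription for anticoagulation". That covers any fill over 2006–2015, not prior-year use in the randomized cohort, so I show a range.

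| s | Delayed | Early | Difference (points) | Risk ratio | Odds ratio |
|---|---|---|---|---|---|
| 0 | 33.0% | 38.0% | 5.0 | 1.15 | 1.244 |
| 0.30 | 23.1% | 26.6% | 3.5 | 1.15 | 1.206 |
| 0.52 | 15.8% | 18.2% | 2.4 | 1.15 | 1.185 |
| 0.60 | 13.2% | 15.2% | 2.0 | 1.15 | 1.179 |

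Example for s = 0.60: (0.152/0.848) / (0.132/0.868) = 1.179. The factor (1 − s) cancels from the risk ratio but not from the difference or the odds ratio.

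**3. Power of the diluted analysis.** Take s = 0.60 and 28,000 per arm (80,000 less 30%, halved). The standard error is √[(0.132 × 0.868 + 0.152 × 0.848)/28,000] = 0.00295, so z = 0.020/0.00295 = 6.8 and power exceeds 99.9%. With the number of eligible patients held fixed, adding non-events lowers z by 7% (s = 0.30) to 13% (s = 0.60). The cost appears only at small effects: for 1.5 points at s = 0.52, power is 79%, against 88% in the 38,400 eligible patients (80,000 × 0.48).

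**4. Dilution set against the selection it should reveal.** Illustration only: no true effect, 10% of eligible patients un-mailable with 20% initiation, the rest at 33%, 19,200 eligible per arm. The early mITT arm shows 33.0%. The delayed arm shows 0.9 × 33% + 0.1 × 20% = 31.7%. That is a false difference of 1.3 points, an odds ratio of 1.06 and about 75% rejection. With 5% or 10% un-mailable and 10% to 45% initiation among them, the false odds ratio runs from 0.95 to 1.11. Dilution at s = 0.30 to 0.60 changes the odds ratio by a factor of 1.244/1.206 = 1.03 to 1.244/1.179 = 1.06, which is the same order.

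**5. What the added analysis would show.** If 10% of eligible early patients are un-mailed, have the 33% rate and gain nothing, the early rate is 33% + 0.9 × 5 = 37.5%. The odds ratio is (0.375/0.625) / (0.33/0.67) = 1.22, against 1.24.

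**The case against.** A reader might infer that the as-randomized analysis cannot check the mITT result. The documents do not support that. It compares the full randomized groups, it is a valid test of no effect, and it has over 99.9% power for the planned effect. In the illustration in step 4 its expected difference is zero while the mITT rejects about 75% of the time. Tables 2a and 2S both give n/N by arm, so a reader can also compare crude risk ratios, which this dilution leaves alone. All of this stands. The limit is that the planned adjusted estimates are odds ratios, and those are not on a common footing.

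A reader might also infer that prior-year users cannot have an incident start. That is not established. If any fill after 365 fill-free days counts, a patient whose last fill was 300 days before follow-up could qualify after day 65. The washout might instead be meant to remove prior-year users, and then this dilution is zero. That second reading sits badly with the statement that treated people are included, so the text needs an edit either way.

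Two further points hold in part. SAP section II describes a possible analysis aimed at the address problem, but it is optional and compares patients within the early arm only. And the mITT exclusions are not one-sided throughout: those for death, disenrollment and OAC start apply to both arms. The asymmetry stated outright concerns addresses. For do-not-contact status it follows from the delayed-arm definition, which names no such filter.

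**Conclusion.** The point holds as a limit on comparability. As written, the as-randomized risk difference and odds ratio are attenuated by prior-year OAC users. For shares of 30% to 60%, the difference falls from 5.0 to between 3.5 and 2.0 points and the odds ratio from 1.24 to between 1.21 and 1.18. The share is assumed, and the result rests on reading the washout as keeping such users in the denominator as non-events. The test of no effect, its power for the planned effect and the risk ratio are not undermined, and the primary analysis itself is not altered by this point. What the plan lacks is a committed between-arm estimate that is free of the mailing asymmetry and on the mITT scale. It is worth correcting before database lock.

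**What to change.** Keep the full as-randomized analysis, to which the Protocol is committed. State in SAP section II whether the 365-day washout removes prior-year users, keeps them as non-events, or counts any fill after 365 fill-free days. Give its time zero, the same in both arms, and say that its odds ratio is expected to be attenuated.

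Add, as a supplement, a sensitivity analysis of all randomized patients in both arms who have:
- no OAC fill (one dispensing or 4 INR tests) in the 365 days before randomization;
- no OAC start between randomization and the wave or pseudo-wave date, since refills by such patients could otherwise count as starts;
- no death or disenrollment in that interval, as in SAP section I.F.

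Apply these checks identically in both arms from the locked data. Keep patients whatever their mailing, address or do-not-contact status. Start follow-up at the wave or pseudo-wave date and use the same adjusted model as the primary analysis. The prior-year criterion is fixed before randomization, and the interval checks precede each patient's own mailing, so applying them equally should preserve comparability.

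The cost is SAP wording and one extra filtered run at each Data Partner. The added estimate will be slightly attenuated by un-mailed patients in the early arm (1.22 against 1.24 in the example with 10% un-mailed).
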